Amended version2:	20151005 for FDA modifications 20151216 for IRB AMD002	Removed the saline injection to the contralateral leg (Section 10.4.1); Removed reference to femoral artery for administering vaccines (Sections 9.1 and 10.4.2); Added CBC and CMP blood draw time point in the table of scheduled assessments for leukapheresis screening with ionized calcium and pregnancy testing per Apheresis practice in footnote (Section 12); Clarified "continues to do well" by defining criteria for vaccine therapy if pseudoprogression is suspected and clarified definition of progression vs pseudoprogression (Section 12.7.3); More clearly defined the definition of unacceptable toxicity (Sections 8, 9.1.1, & 15.4.1); Updated the definition of SAE to match 21CFR312.23 (Section 13.2); Added the FDA for all adverse event reporting (Section 13.2.1); Corrected mis-numbering of inclusion criteria (Section 11.1); Added the exclusion of subjects unable to undergo MRI (Sections 11.2 & 12.8.2); Removed the word "transmural" from the 4 th exclusion criterion (Section 11.2); Removed ACD description of red top tubes (Section 12); Added an additional clinic visit with blood work to assess for delayed toxicity 1 month following last
Amended version 3	20151216 for IRB AMD002	vaccine (Section 12). Removed exploratory objective comparison to historical controls (Section 8); Better described evaluable subjects (Sections 9.4 and 15.4.2); Updated location of paper documents (Section 0); Changed DLT to unacceptable toxicity (12.6.1); Removed statistical estimate (Section 15.4.2)
Amended version 4	20160201 for IRB AMD004	Added investigators [name] & [name] to cover page. Typographical error corrected in Section 11 for inclusion criterion on KPS score from 60 to 70%. Changed wording from "recurrent" to "progressive" (Sections 8, 9, 11, 12, and 15). Removed the prior chemotherapy exclusion criterion (Section 11).
Amended version 5	20160517 for IRB AMD010	Updated eligibility criterion on pregnancy testing to within 72 hours prior to leukapheresis (Section 11).
Amended version 6	20160519 for IRB AMD011	Clarified difference between Td booster and pre-conditioning by adding route of administration as well as changed booster for ALL subjects (Sections 6, 9, 10, & 12); Allowed subjects that transition to a higher grade glioma to continue on vaccines monthly during SOC XRT/TMZ (Sections 6, 8, 9, 12, and 15); Updated immune monitoring blood work and

		biomarker testing and removed urine sampling (Sections 6, 8, 9 12, & 15); Added genomic analyses (Sections 8, 9, 12, and 15); Added MRS for 2HG measurements (Sections 6, 8, 9, 12 & 15); Changed wording from specifically study coordinator to study team (Section 9); Included standard language for leukapheresis preparation (Section 12); Increased the dexamethasone from 2 mg to 4 mg max (Section 12); clarified KPS and physical exam to occur during standard BTC visit with the Td pre- conditioning (Section 12); clarified tumor sampling for IHC analysis (Section 12); added language regarding antihistamine usage (Section 12); Included SOC language for XRT/TMZ and adjuvant TMZ in the appendices as a reference (Sections 18.4 & 18.5).
Amended version 7	20160808 for IRB AMD015	Adjusted timing of immune monitoring and genomic proteomic analysis in those who've transformed to a higher grade (Sections 6, 9.4, and 12); Clarified the description of study procedure following consent (Section 9); Clarified pregnancy testing and MRIs in table of events as well as pathology testing (Section 12); Corrected error in timing of vaccine #1 (Section 12); allowed for every 3 month MRI in low grade setting (Section 9 and 12); Updated screening examination to match current practice and updated location of paper CRFs (Section 12); and Corrected error that vaccine #3 is actually given on day 29 not day 30 (Sections 6, 9, and 12).
Amended version 8	20161128 for IRB AMD023	Formatted for FDA electronic submission; Changed the lead study coordinator and regulatory coordinator; Reformatted Table 2: Screening and On-Study Tests and Procedures (Section 12); Clarified that vaccine will be given on day 22 (+2), not day 21 (+/-2) of monthly cycles of TMZ because vaccine cannot be given on the same day as TMZ (Section 6, throughout); Clarified that Single-Voxel MR will be done before Td booster (Section 6, Section 9.5); Removed requirement that leukapheresis be performed within 2 weeks of consent (Section 9.1, Section 12); Corrected guidelines for dose delay, reduction, and discontinuation to fit 21-day TMZ, not standard 5-day TMZ (Section 18.5.2); Grade 3 subjects receiving RT/TMZ can delay TMZ more than a week without coming off study (Section 18.5.1); Corrected CTQA to the new name OARC (Section 4, Section 14.2); Immunization mixture will be given half in right groin and half in left groin for each vaccine (Section 9.1, Section 10.4.2, Table 2); Changed SOC abbreviation to standard of care, not Safety Oversight Committee (Section 12.3)
Amended version 9	20170106 for IRB AMD027	(Section 13.3) Added additional MRS time points (Sections 6, 9.1, 9.5, 12); Corrected MRS

		1-2 hours (Section 9.5); Baseline MRS is before PEP _{IDH1M} vaccine #1 (Section 9.5)
Amended version 10	20170127 for IRB AMD030	Removed recommendation that the needle be 25 gauge for injection of study vaccine because it is too narrow a bore for the vaccine (Section 10.4.2); Added that EMLA ® cream, or equivalent topical analgesic, can be offered to subjects who experience local pain at the injection site (Section 12.8.2); Corrected the number of patients to 24 in the Study Schema (Section 6); Testing of leukapheresis blood for HIV, hepatitis, and syphilis was re-moved (Section 12.8.2)
Amended version 11	20170215 for IRB AMD035	Added immune monitoring time point at vaccine #6 (Sections 6, 9.1, and 12)
Amended version 12	20170223 for IRB AMD037	Changed Principal Investigator (title page, Section 13.2.1)
Amended version 13	20171011 for IRB AMD054	Primary objective wording changed from "proportion" to "percentage" (Sections 8 and 15.4.1); Changed wording of the timing of the Td from "12-24 hours" before vaccine #1 to "one day" before (Sections 6, 9.1, 10.4.1, and 12); Clarified documentation of review of aggregate summary of AE information (Section 13.1.1); Added that providers will take pictures of the injection site at clinic visits at pre-op time point and at other time points at discretion of physician (Sections 9 and 12); Added collection of research blood at end of vaccine treatment (1 month after vaccine #15 or time the subject comes off study, whichever comes first) (Section 12): Changed total enrollment from 24 to 28, keeping the number of evaluable subjects that will receive at least 6 vaccines at 20 (Sections 6 and 15.4.2)

4 LIST OF ABBREVIATIONS

2HG	R-2-Hydroxyglutarate
Ab	Antibody
ABC	Automated Blood Count
ACD	Acid Citrate Dextrose
ACLS	Advanced Cardiac Life Support
ACTH	Adrenocorticotropic Hormone
AE	Adverse Event
αKG	Alpha-ketoglutarate
AML	Acute Myeloid Leukemia
APAAP	Alkaline Phosphatase Antialkaline Phosphatase Complex
ALT	Autologous Lymphocyte Transfer
ANC	Absolute Neutrophil Count
AST	Aspartate Aminotransferase
AT	Ambient Temperature
BBB	Blood Brain Barrier
β-HCG	Beta-Human Chorionic Gonadotropin
BMT	Bone Marrow Transplant
BTC	Brain Tumor Center
BUN	Blood Urea Nitrogen
Ca++	Calcium
caBIG®	Cancer Biomedical Informatics Grid
CAMRD	Center for Advanced MR Development
CAR	Chimeric Antigen Receptor
CBC	Complete Blood Count
CCL3	C-C motif Chemokine Ligand 3
cDNA	Complimentary Deoxyribonucleic Acid
CFA	Complete Freund's Adjuvant
CFC	Cytokine Flow Cytometry
CLIA	Clinical Laboratory Improvement Act
CMP	Comprehensive Metabolic Panel
CNC	Clinical Neurologic Change
CNS	Central Nervous System
CPC	Cancer Protocol Committee
CIMP	CpG-Island Methylator Phenotype
CRF	Case Report Form
СТ	Computed Tomography
CTCAE	Common Terminology Criteria for Adverse Events
CTL	Cytotoxic T-Lymphocyte
DAR	Drug Accountability Record
DBTIP	Duke Brain Tumor Immunotherapy Program
DC	Dendritic Cell
DCCC	Duke Comprehensive Cancer Center
DCI	Duke Cancer Institute
DOB	Date of Birth
DSMB	Data and Safety Monitoring Board
DSMP	Data and Safety Monitoring Plan
DTH	Delayed-type Hypersensitivity
DUHS	Duke University Health System
EAE	Experimental Autoimmune Encephalomyelitis
EBRT	External Beam Radiation Therapy
eCRFs	Electronic Case Report Forms
ELISA	Enzyme-Linked ImmunoSorbent Assay

ELISPOT	Enzyme-linked Immunospot	
EGFR	Epidermal Growth Factor Receptor	
EGFRvIII	EGFR variant III	
FACS	Fluorescence Activated Cell Sorting	
FDA	Federal Drug Administration	
FEV	Forced Expiratory Volume	
GBM	Glioblastoma	
GCP	Good Clinical Practice	
GLP	Good Laboratory Practice	
GM-CSF	Granulocyte Macrophage Colony Stimulating Factor	
HIV	Human Immunodeficiency Virus	
HLA	Human Leukocyte Antigen	
HMG	Hemoglobin	
HMO	Health Maintenance Organization	
HPLC	High Pressure Liquid Chromatography	
IBA	Ion Beam Applications	
IC		
_	Intracerebral(ly)	
ICF ICH	Informed Consent Form International Conference on Harmonization	
IDH1	Isocitrate Dehydrogenase 1	
IEC	Independent Ethics Committee	
IFA	Incomplete Freund's Adjuvant	
IFN-γ	Interferon-gamma	
IHC	Immunohistochemistry	
IL-4	Interleukin-4	
IL-12	Interleukin-12	
IL-13	Interleukin-13	
IRB	Institutional Review Board	
KLH	Keyhole Limpet Hemocyanin	
KPS	Karnofsky Performance Status	
LAL	Limulus Amoebocyte Lysate	
LGG	Low Grade Glioma	
MAb	Monoclonal Antibody	
MedDRA	Medical Dictionary for Regulatory Activities	
MG	Malignant Glioma	
MHC	Major Histocompatibility Complex	
MRI	Magnetic Resonance Imaging	
MRN	Medical Record Number	
mRNA	Messenger Ribonucleic Acid	
MRS	Magnetic Resonance Spectroscopy	
MTD	Maximally Tolerated Dose	
NA	Non-adherent	
NCI CTC	National Cancer Institute Common Toxicity Criteria	
NIH	National Institutes of Health	
NK	Natural Killer	
OARC	Office of Audit, Risk, and Compliance	
OS	Overall Survival	
PBL	Peripheral Blood Lymphocyte	
PBMC	Peripheral Blood Mononuclear Cells	
PBS	Phosphate-Buffered Saline	
PET	Positron Emission Tomography	
PD	Progressive Disease	
PHA	Phytohemagglutinin	
FHA		

PFS	Progression Free Survival					
PI	Principle Investigator					
PRTBTC	Preston Robert Tisch Brain Tumor Center					
PT	Prothrombin Time					
PTT	Partial Thromboblastin Time					
PTMs	Post-Translational Modifications					
QC/QA	Quality Control/Quality Assurance					
R-2HG	R-2-hydroxyglutarate					
RANO	Revised Assessment in Neuro-Oncology					
RDSPs	Research Data Security Plans					
RECIST	Response Evaluation Criteria in Solid Tumors					
reGBM	Recurrent Glioblastoma					
reLGG	Recurrent Low Grade Glioma					
RIO	Research Integrity Office					
RNA	Ribonucleic Acid					
RT	Radiation Therapy					
RT-PCR	Reverse Transcriptase Polymerase Chain Reaction					
SAE	Severe Adverse Event					
scFV	Single Chain Variable Antibody Fragment					
SFC	Spot-Forming Cells					
SOC	Standard of care					
SOP	Standard Operating Procedure					
SPECT	Single Photon Emission Computed Tomography					
TCA	Trichloroacetic Acid					
TCR	T cell Receptor					
Td	Tetanus-diphtheria toxoid					
TGF-β	Transforming Growth Factor-β					
TMZ	Temozolomide					
TNF-α	Tumor Necrosis Factor-α					
T _{regs}	Regulatory T cells					
TTP	Time to Progression					
TTRNA	Total Tumor mRNA					
VDLNs	Vaccine-site Draining Lymph Nodes					
WHO	World Health Organization					
WOCBP	Women Of Childbearing Potential					
XRT	Radiation Therapy					

5 PROTOCOL SYNOPSIS AND SUMMARY

Please see separate document (available upon request).

6 STUDY SCHEMA

[figure not shown]

Figure 1. Study Schema

7 BACKGROUND AND SIGNIFICANCE

7.1 Study Disease

Malignant primary brain tumors are the most frequent cause of cancer death in children and young adults and account for more deaths than cancer of the kidney or melanoma.³ Gliomas are the most common primary brain tumors with GBMs, astrocytomas and oligodendrogliomas comprising the large majority of subtypes.⁴ Primary GBM, WHO grade IV, occurs *de novo* and is the most common and aggressive glioma with a median OS of <15 months.⁵ Patients with lower grade II or III astrocytomas, oligodendrogliomas or mixed gliomas have a more favorable OS. However, lower grade astrocytomas can progress to secondary GBM and malignant progression is assured in almost all cases with patients succumbing to disease within a decade. Moreover, current therapy for malignant primary brain tumors is incapacitating⁶ and limited by non-specific toxicity to systemic tissue or surrounding eloquent brain.

In contrast, immunotherapy promises an exquisitely precise approach and substantial evidence suggests that immunotherapeutic intervention can eradicate well-established tumors in mice and humans, even when tumors reside within the "immunologically privileged" brain. (See Figure 2, Figure 3, and Figure 4)^{1,2,7,8} There is a clear and urgent need for the development of targeted therapeutics that can improve outcomes for patients with glioma without adding significant toxicity to current treatment regimens. Immunotherapy targeting tumor-associated antigens holds significant promise to meet this need.

[figure not shown]

Figure 2. Highly reactive transferred cells traffic to brain and destroy tumor deposit in melanoma patients. Arrows represent location of melanoma metastases. (From Johnson *et al.*, Blood 2009)¹

[figure not shown]

Figure 3. Host-derived antitumor T cells treat lesions in the brain. Arrows represent location of metastases. (A&C) Pretreatment (B) 14 months after cell transfer (D) 6 months after cell transfer. (From Hong et al., Clinical Cancer Research)²

[figure not shown]

Figure 4. Genetically engineered antitumor T cells treat lesions in the brain Arrows represent location of metastases. (A&C) Pretreatment (B) 6 months after cell transfer (D) 30 months after cell transfer. (From Hong et al., Clinical Cancer Research)²

7.2 Study Agents

The study agent will consist of a 25 amino acid peptide (PEP_{IDH1M}) and the adjuvants GM-CSF and Montanide ISA-51.

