Our Td pre-conditioning platform in the context of DC vaccination also elicited superior anti-tumor responses compared to controls receiving DC vaccines without Td pre-conditioning. In our clinical trial, patients with newly-diagnosed GBM who were administered the Td skin prep before DC vaccination revealed significantly longer progression-free and overall survival rates compared to the control cohort. In evaluating the relationship between DC migration and clinical responses, we observed a modest positive correlation between levels of DC migration and survival. In our preclinical model, Td pre-conditioning prior to vaccination with tumor antigen-specific DCs dramatically suppressed the growth of established and highly aggressive B16-F10/OVA tumors. The use of Td with a DC vaccine increased antitumor responses in an antigen-specific manner, as non-specific DC vaccines were not potentiated with Td pre-conditioning. Furthermore, in a challenge setting, where mice are administered the treatment platform prior to challenge with tumor inoculation, Td pre-conditioning at the vaccine site induced a significant survival benefit compared to controls.

For this clinical trial evaluating PEPIDH1M, we are also proposing to use Td as an adjuvant based on the pre- clinical data described below. Here, mice were immunized with 25mer mutant and wildtype peptides with two clinically relevant adjuvants: granulocyte-macrophage colony stimulating factor (GM-CSF), a

cytokine known to have a principle role in the activity of antigen presenting cells, and imiquimod, a topical TLR7 agonist administered at the vaccine site and tetanus-preconditioning. Immunogenicity of each adjuvant/vaccine combination was measured via IFNγ ELISpot; administration of imiquimod at the site of vaccination results in a more robust mutant-specific immune response compared to GM-CSF, Notably, immunogenicity of the mutant peptide in mice that received imiquimod emulsified in IFA/IFA/IFA is comparable to the immune response seen in mice that received CFA/IFA/IFA, a treatment course with widely known strong adjuvant activity (Figure 5).

[figure not shown]

Figure 5. Tetanus pre conditioning, imiquimod and GM-CSF increases the number of IDH1 mutant specific T cells after vaccination. Mice were immunized with (three weekly 100 ug of peptide emulsified in IFA/IFA/IFA), and immunogenicity was measured via IFNγ ELISPOT against both the wild-type and mutant 25mer peptides.

7.2.5 **Pre-clinical experience**

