10.3 Supply, Receipt, and Storage

The PEP_{IDH1M} will be manufactured under GMP conditions by Bachem Americas, Inc., and stored in the investigational pharmacy. Montanide is supplied by Seppic and stored at 4°C in the investigational pharmacy.

GM-CSF (LEUKINE®; sargramostim) will be obtained from commercial supply, as a sterile, white, preservative-free powder lyophilized powder in a vial containing 250 mcg to be reconstituted in 0.5 mL of sterile water for injection.

Store GM-CSF under refrigeration at 2-8°C (36-46°F). Vials must not be frozen.

Lyophilized GM-CSF vials contain no antibacterial preservative, and therefore solutions prepared with Sterile Water for Injection, USP should be administered as soon as possible, and within 6 hours following reconstitution. The vial should not be re-entered or reused. Do not save any unused portion for administration more than 6 hours following reconstitution. Bacteriostatic Water for Injection, USP (0.9% benzyl alcohol) should NOT be used.

Aseptic technique should be employed in the preparation of all GM-CSF solutions. To assure correct concentration following reconstitution, care should be exercised to eliminate any air bubbles from the needle hub of the syringe used to prepare the diluent. During reconstitution of lyophilized GM-CSF, the diluent should be directed at the side of the vial and the contents gently swirled to avoid foaming during dissolution.

PEP_{IDH1M} will be stored at -80°C, thawed, and inspected visually for particulate matter and discoloration prior to administration. If particulate matter is present or the solution is discolored, the vial should not be used. Before use, the vial should be gently swirled to ensure uniform mixing of the contents. Avoid excessive or vigorous agitation; do not shake.

Td is indicated for active booster immunization against tetanus, diphtheria, and pertussis as a single dose; substitute 1-time dose of Tdap for Td booster, then standardly boost with Td every 10 years. Please refer to section 7.2 on the use of Td in this protocol. This study agent Td (Tetanus diphtheria toxoid adsorbed) is supplied by Duke Pharmacy and stored at 4°C.

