10.4 Dispensing, Preparation and Administration

10.4.1 Td

The Td booster vaccine will be administered at the initial consent visit only after the subject has signed consent. Administration will be done as per standard of care and according to package insert instructions (please see appendices in Section 18) with 0.5 mL of Td (tetanus and diphtheria toxoids adsorbed) I.M. into the deltoid muscle. In addition, vaccine site pre-conditioning will be performed as a single dose of Td toxoid (1 flocculation unit, Lf, in a total volume of 0.4 mLs saline) administered i.d. to the RIGHT side of the groin one day prior to the first vaccine.

10.4.2 PEP_{IDH1M} Vaccine with GM-CSF and Montanide ISA 51

The PEPIDH1M vaccine and GM-CSF will be mixed with Montanide ISA 51 (shortened to PEPIDH1M vaccine for the other sections of this protocol) in the investigational pharmacy and will be delivered directly to the bedside under the supervision of the research nurse. Vaccines will be administered according to

protocol. The patient's name, Study ID, DOB, and MRN will be double verified prior to vaccine administration.

PEPIDH1M will be co-administered with GM-CSF and mixed 1:1 with Montanide ISA 51.

Lyophilized GM-CSF should be reconstituted with Sterile Water for Injection, USP. Bacteriostatic Water for Injection, USP (0.9% benzyl alcohol) should NOT be used. During reconstitution, the diluent should be directed at the side of the vial and the contents mixed by gently swirling to avoid foaming during dissolution. Avoid excessive or vigorous agitation; do not shake.

Each vial of lyophilized GM-CSF (250 mcg/vial) should be reconstituted with 0.43 ml of Sterile Water for Injection, USP 0.35 ml of reconstituted GM-CSF will be withdrawn, under aseptic conditions, using a hypodermic needle and syringe.

Each vial of PEPIDH1M will be thawed at room temperature PEPIDH1M should fully thawed within 0.5 to 3 minutes, with no remaining visible frozen drug or particulate. The resultant solution of PEPIDH1M (0. 4 ml of 2.0 mg/ml PEPIDH1M) is a clear and colorless solution.

The syringe with the previously withdrawn GM-CSF (0.35 ml volume containing 203 mcg GM-CSF), will be used to withdraw 0.35 mL of peptide. The aqueous peptide/GM-CSF is mixed 1:1 with 0.7 mL of Montanide ISA 51 according to the manufacturer's instructions. One mL of the mixture will be administered by intradermal injection (in divided doses) in the patient's groin.

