13.1 Adverse Events

An AE is any untoward medical occurrence in a subject receiving study drug and which does not necessarily have a causal relationship with this treatment. For this protocol, the definition of AE also includes worsening of any pre-existing medical condition. An AE can therefore be any unfavorable and unintended or worsening sign (including an abnormal laboratory finding), symptom, or disease temporally associated with the use of the PEP_{IDH1M} and GM-CSF, whether or not related to use of the vaccine. Abnormal laboratory findings without clinical significance (based on the PI's judgment) should not be

recorded as AEs. But laboratory value changes that require therapy or adjustment in therapy are considered adverse events. All lab values that are not deemed AEs by the PI will be noted to be Non-Clinically Significant in the subject record and source documents.

From the time the subject signs the informed consent form through the End of Treatment visit (as defined in Sections 12.3, 12.5 and 12.6), all AEs must be recorded in the subject medical record and electronic adverse events case report form.

AEs will be assessed according to the CTCAE version 4.0. If CTCAE grading does not exist for an AE, the severity of the AE will be graded as mild (1), moderate (2), severe (3), life-threatening (4), or fatal (5). Attribution of AEs will be indicated as follows:

- Definite: The AE is clearly related to the study drug
- Probably: The AE is likely related to the study drug
- Possible: The AE may be related to the study drug
- Unlikely: The AE is doubtfully related to the study drug
- Unrelated: The AE is clearly NOT related to the study drug

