15.4.1 Variable

The percentage of patients with an unacceptable toxicity will be estimated, where unacceptable toxicity is defined as any Grade 3 toxicity at least possibly attributed to the vaccine (or vaccine + TMZ and/or RT) that does not resolve to baseline within 3 weeks, any Grade 3 hypersensitivity reactions requiring steroids, any Grade 4 toxicity, including neurologic events not due to progressive disease, or any life threatening-event not attributable to concomitant medication, co-morbid event, or disease progression.

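### A persistent Grade 3 event judged due only to intradermal Td is recorded but not counted in the primary percentage or suspension rule, and the documents disagree on whether Td is a study agent

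*Combined protocol and SAP*

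**What the plan says.** The combined protocol and SAP gives intradermal Td two incompatible positions.

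- **Left out.** Section 7.2: "The study agent will consist of a 25 amino acid peptide (PEP_{IDH1M}) and the adjuvants GM-CSF and Montanide ISA-51". Section 10.1 names the drug as the PEPIDH1M vaccine, and 10.4.2 says the mixture of those three components is "shortened to PEPIDH1M vaccine for the other sections of this protocol". Section 16.9 lists the study drug and Td as separate cost items.
- **Included.** Td has its own subsection, 7.2.4, under the Study Agents heading, with the statement "we are also proposing to use Td as an adjuvant". Section 10.3 reads "This study agent Td (Tetanus diphtheria toxoid adsorbed) is supplied by Duke Pharmacy and stored at 4°C". Td administration is described in 10.4.1, inside the study drug chapter.

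The pre-conditioning dose is a trial step, distinct from the standard-of-care intramuscular booster given after consent. It is "administered i.d. to the RIGHT side of the groin one day prior to the first vaccine" (10.4.1). Half of every vaccine dose then goes into that same groin (10.4.2).

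On safety, 13.1 defines an adverse event by its timing relative to use of the peptide "and GM-CSF, whether or not related to use of the vaccine", and scores causality against the study drug only. The first criterion for unacceptable toxicity in 15.4.1 is "any Grade 3 toxicity at least possibly attributed to the vaccine (or vaccine + TMZ and/or RT"), when the event has not returned to baseline in 3 weeks; Table 1 and 9.1.1 are equivalent. Section 9.6 ties evaluability of patients who stop early to an event caused by, or related to, vaccination. The death trigger in 15.4.2 names vaccine alone or vaccine and TMZ. Section 15.4.3 removes anyone who received no vaccine from all analyses. None of these names Td.

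**The concern.** The primary objective is safety, and the plan itself describes Td as an adjuvant to the vaccine. Every patient is to receive it because of the trial. If toxicity put down to this step is not counted, the primary percentage and the accrual rule describe only part of what patients were given.

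The contradiction over Td's status adds an attribution problem. An assessor who follows 10.3 can score a right-groin reaction as related to a study agent; one who follows 7.2 and 10.4.2 can score the same reaction as unrelated to the vaccine. Timing may not settle it. Under 12.7.2 only vital signs are taken at vaccine #1, so the next scheduled physical examination after the Td visit is at vaccine #2, on day 15 ±3.

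**Working it through.** The plan gives no figure on this point, so the check is mainly of wording, followed by short arithmetic.

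**Step 1. Are Td events recorded?** Yes. Section 9.1 collects all adverse events from consent, which precedes both Td doses. Section 13.1 requires no causal link. Section 13.1.1 summarises all events, related or not. Table 2 marks AE/SAE collection at the visit one day before vaccine #1, which is the Td visit.

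**Step 2. Are they counted?** Each kind of event after intradermal Td, taken through the definitions as written:

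| Event | Vaccine-attribution test? | Result |
|---|---|---|
| Grade 4 toxicity | No | Unacceptable toxicity |
| Grade 3 hypersensitivity requiring steroids | No | Unacceptable toxicity |
| Grade 3 beyond 3 weeks, possibly vaccine-related | Yes, met | Unacceptable toxicity |
| Grade 3 beyond 3 weeks, judged due to Td and not even possibly to vaccine | Yes, not met | Not in the primary numerator or the Table 3 count |
| Any event that prevents vaccine #1 | Not reached | Excluded from all analyses (15.4.3) |

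In the fourth row, a patient who reaches 6 vaccines stays in the denominator as a patient without unacceptable toxicity. One who stops earlier is not evaluable and is replaced (15.1, 15.4.2).

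**Step 3. Do the first two rows hold for a patient who stops early?** The sections conflict. Sections 15.1 and 15.4.2 keep any patient with an unacceptable toxicity. Section 9.6 keeps such a patient only if the event was due to one of the first 3 vaccinations (six-patient review) or related to vaccine or vaccine + TMZ (final analysis). For the last row, 12.6.2 classes a patient withdrawn before vaccine treatment as an eligibility failure. Section 12.6.3, by contrast, does not replace such a patient if an unacceptable toxicity occurred.

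**Step 4. Size.**

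- Input: 20 evaluable patients (15.4.2). With x counted events the estimate is x/20. With one Td-only event also counted it is (x + 1)/20. The difference is 1/20 = 0.05, or 5 percentage points. It is the same whether the patient stays in as a non-event or is replaced by a patient without an event.
- Six-patient review (15.4.2): accrual continues if 2 or fewer patients have an unacceptable toxicity. Two vaccine-attributed events plus one Td-only event are read as 2, so accrual continues. Counted together, 2 + 1 = 3, and protocol modifications are considered before more patients are accrued. This illustrates the rule; no likelihood is attached to it.
- Probability of an omitted event: not calculable. It would need the rate of Grade 3 events that last beyond 3 weeks and are judged not even possibly vaccine-related. The documents give no such rate.

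**The case against.** The strongest reply is that the attribution test matches the stated objective, which is the safety of the PEPIDH1M vaccine alone and with TMZ and/or RT. On that view, leaving Td out is a legitimate choice. It would be, if stated consistently; but the plan also calls Td an adjuvant and a study agent, so a reader cannot tell that the exclusion was intended.

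A second reply is that the gap is very small. This largely stands. The bar is only possible attribution. Td is given once, the day before vaccine #1, and vaccine #2 follows on day 15 ±3. By the time a reaction has lasted 3 weeks in a patient on schedule, the same groin has received vaccine twice, and many local events would be called at least possibly vaccine-related. Section 12.8.2 describes Td pain and discomfort as lasting up to three days, and 15.4.2 expects few or no unacceptable toxicities before surgery. These points make the omission rare; they do not close it, and they do not reach the patient who never receives vaccine #1.

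A reader might infer from 13.1, which names only the peptide and GM-CSF, that Td reactions escape adverse-event collection. Step 1 shows that they do not. Nor do the documents support saying that Td simply lies outside the study agent: 10.3 and the placement of 7.2.4 say the opposite, so this is a contradiction to reconcile.

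**Conclusion.** The point holds in a limited form. Followed as written, the rules omit a persistent Grade 3 event judged due to intradermal Td alone from the primary percentage and the suspension count, and they drop from all analyses a patient whose Td reaction prevents vaccine #1. The death trigger likewise does not name Td. Each omitted patient is worth about 5 points, assuming that the target of 20 evaluable patients is met.

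A reader might infer that severe Td toxicity in general goes uncounted. That is not supported: Grade 4 events and Grade 3 hypersensitivity requiring steroids are unacceptable toxicities without any vaccine-attribution test, subject to the conflict between 9.6 and 15.1/15.4.2 for early stoppers. A reader might also want a probability that the percentage is understated. Any such figure would rest on an invented rate, so none is given. The inconsistency should be corrected, but it does not undermine the primary endpoint as a whole.

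**What to change.** 1. Reconcile 7.2, 10.1, 10.3, 10.4.2 and 13.1 on whether intradermal Td pre-conditioning belongs to the investigational regimen.
2. Align the attribution wording in Table 1, 9.1.1, 9.6, 13.1, 15.4.1, 15.4.2 and 15.4.3, so that toxicity at least possibly due to the vaccine or to its intradermal Td pre-conditioning is counted. At minimum, tabulate Td-attributed toxicity beside the primary percentage, including patients who received intradermal Td but no vaccine.
3. Add one attribution field for intradermal Td to the adverse-event form, kept separate from the standard-of-care intramuscular booster.
4. Do not use right-versus-left groin reactions to measure Td's contribution. Only the right groin is pre-conditioned, but 7.2.4 reports that one-sided Td raised dendritic-cell migration to both inguinal nodes equally, so the left groin is not a clean control.

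The cost is protocol wording and one form field, with no change to any dose, schedule or procedure. The downside is that the reported toxicity percentage may be slightly less favourable.
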